## **Study Participants:**

The study includes the following participants:

### **Newborn-mother pairs in the community reached by the intervention teams (Counseled mothers)**

Parishes will be randomized to receive an outreach intervention. Pregnant and postpartum women and their families will be the focus of this outreach conducted at community events, religious services, and in individual home visits by both religious leaders and members of the Health Development Army. Priest and HDA trainees in the study will be trained to discuss the topics of newborn care with pregnant women and their families. Priests and HDA members will offer women and their families an opportunity to decline individual counseling on these topics as part of their scripted protocol.

### **Newborn-mother pairs approached to enroll in prospective follow-up (Enrolled women and newborns)**

The LAUNCH study team will collect individual-level data from each participating newborn-mother pair in the trial to measure exclusive breastfeeding, vaccination coverage, anthropometry, community engagement, and other indicators of maternal and child health.

## **Inclusion and Exclusion Criteria:**

### Inclusion Criteria:

#### **Newborn-mother pairs visited by the study staff (Enrolled women and newborns)**

The following inclusion criteria will be used during recruitment:

- Newborns should be those delivered at least one month after the start of the intervention period
- Newborn-mother pairs will include only biological mothers
- Newborn-mother pairs should be EOC parishioners
- Newborn's family should have a soul father (a spiritual advisor assigned to the family in the Ethiopian Orthodox tradition)
- Mother must have lived in the study area for at least 6 months
- Mothers must give written informed consent for themselves and their newborn

### Exclusion Criteria:

#### **Newborn-mother pairs visited by the study staff (Enrolled women and newborns)**

The following exclusion criteria will be used during recruitment:

- Newborns with gross developmental abnormalities that would make anthropometric measurements and interpretations difficult
- Newborn whose mother is not a member of an EOC parish

- Newborns whose mothers have died by the time of recruitment
- Newborn whose family plans to re-locate away from the study site in less than 6 months

**Number of Subjects:**

Group name/description	Desired number of individuals (or other subject unit) who will complete the research
Newborn/Mother Pairs	240

**Procedures:**

The intervention in this study is intimately tied to the cultural customs and values of the North Gondar region of Ethiopia. In this region, religious leaders of the Orthodox Church have the potential to be strong advocates or hindrances to effort to improve public health and this study aims to explore how linking religious leaders to frontline health workers may catalyze and empower local communities to improve health outcomes for newborns. The study engages several experienced Ethiopian investigators and will seek continual input from a Steering Committee of community members in Gondar to ensure that all elements of the study are culturally appropriate and conducive to the local context.

Newborn-mother pairs will be recruited within the first 10 days after delivery as reported to the study team by Health Extension Workers (HEWs) engaged in the study. Recruitment will start one month following the start of the intervention and all reported newborn-mother pairs who meet the screening criteria will be included in the study until the calculated sample sizes are reached. HEW's routine registers of new deliveries will be used to trace, recruit and screen study participants. Newborn-mother pairs who fulfill an initial screening criteria will be reported to the study team at the University of Gondar (UoG) who will travel to the study site regularly for recruitment of study participants and data collection. Newborn-mother pairs will be reported to the UoG study team both through phone calls made by HEWs and in-person at the time of regular onsite visits by the team.

Eligible newborn-mother pairs will be visited by a member of the study team at their home or at an appointed meeting location in their community to complete the verbal informed consent process. Those pairs who attend church at a parish that received the intervention will be assigned to the intervention arm, and those from the parishes where no intervention was conducted will be assigned to the control arm. Initial baseline data will then be collected and follow-up visit schedules arranged with the study team.

The following materials will be used during the recruitment of study participants:

- Oral consent scripts (see attached scripts) will be used to provide information about the study to potential subjects.
- A checklist of the initial screening criteria will be used by the HEWs and study team to identify appropriate newborn-mother pairs.

No payment will be provided for participating in the study. Some women may be eligible to receive a travel reimbursement (including transportation and meal stipend) to compensate them for attending scheduled meetings for study follow-up. The maximum value of a travel reimbursement will be \$5. In special cases, women travelling longer distances may be compensated to a greater degree on a case by case basis. Non-monetary compensation may include refreshments provided by the study at focus group

discussion, meetings, and gatherings. Participating infant-mother pairs will also have basic anthropometric measurements taken by the study staff free of charge, which some participants may view as a benefit of participation.

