## Methods:

### Study Design:

In collaboration with the woreda administrative office and the woreda diocese of the EOC, all the kebeles and EOC churches in the woreda will be mapped by the study team and randomly assigned to intervention or control. Sites will be selected in a way that ensures they are reasonably far apart in order to avoid contamination. Newborn-mother pairs in the catchment areas of the intervention churches will receive the intervention, whereas those in the control churches will receive routine community health packages implemented by community health workers (HEWs and HDAs).

The intervention will be implemented at the community level by pairs of trained EOC priests and members of the HDA. A list of priests serving at the EOC churches in the intervention arm will be obtained through the woreda diocese and their respective churches. All the priests will be contacted through the church leadership and asked to participate in the study intervention. The intervention will be implemented in collaboration with HDA members recruited by HEWs under the health centers in the catchment areas of the intervention churches. HDA members 55 years old or younger will be asked to participate.

An initial 5-day training will be given to priests and HDA members. The training will focus on newborn health topics including early initiation of and exclusive breastfeeding, maternal nutrition, immunization, childhood illnesses, child health care services, etc. At the end of the training action plans will be prepared by the training organizers, priests, and HDA. Priest will be asked to integrate health messages

---

 Central Statistical Agency - CSA/Ethiopia and ICF. 2017. Ethiopia Demographic and Health Survey 2016. Addis Ababa, Ethiopia: CSA and ICF. Available at <http://dhsprogram.com/pubs/pdf/FR328/FR328.pdf>.

and education into their routine family visits around the birth of a child in structured intervals as culturally appropriate.

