The trained priests and HDA members will be dispatched to their respective communities to begin the intervention. Their primary activities will be identification of near-term pregnant and newly delivered women, providing health education to their families, follow-up visits to enable newborn-mother pairs to access child health care services, and to provide health education at religious and community gatherings. Specifically, pre-planned visits of parishioners' families will be done by the respective priests and the partnering HDA members during the last month of pregnancy, immediately after the delivery of the baby and around the time of baptism for the newborn. These visits will be used to educate pregnant and postpartum women and their families on newborn health topics including initiation of breastfeeding, duration of breastfeeding/ exclusive breastfeeding, vaccination, cord care, and utilization of available newborn health care services. These community-based activities will be monitored through regular follow-up visits by the UoG study team and discussions with priests and HDA members.

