### **Prospective follow-up**

Research assistants will work for the zonal health office to identify all births occurring in the study area. Independent of the intervention outreach teams, the research assistants will attempt to contact all newborn-mother pairs within 10-days of birth. Most contacts will occur at home, but contact may be made at other locations (e.g., health facility, church). Mothers will be invited to participate in the study, and each participating newborn-mother pair will be followed-up by the study team for up to 6 months after enrollment.

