### **Data Collection**

The UoG study team will conduct regular visits in both the intervention and control communities to screen, consent, and register new newborn-mother pairs reported by HEWs, collect baseline data from them, arrange follow-up visit schedules, and collect follow-up data from previously enrolled study participants. Each newborn-mother pair will receive up to three visits by the study team in the sixth month period. The study team will use OpenDataKit (ODK), an electronic data collection system to record data on tablets. The study team will upload the collected data to a secured central web-based server upon return to the UoG campus. The overall processes of recruitment and subsequent data collection activities will be supervised by an on-site study manager. The study team will rely heavily on pre-designed standard operating procedures that contain detailed, step-by-step instructions for collecting and handling data.

The following primary and secondary outcome variables will be assessed in this study:

**Primary outcome variables:** mid-upper arm circumference (MUAC), proportion of mothers exclusive breastfeeding

**Secondary outcome variables:** immunization status (complete vaccination and individual vaccines), frequency of acute illnesses, and frequency of hospitalization

**Predictors (other than intervention):** maternal age, sex of child, maternal education, family economic status, family size, etc.

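### The plan gives two different sampling frames for births, and the one that relies on pre-screening by health extension workers after allocation could let recruitment differ by arm

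*Combined protocol and SAP*

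**What the plan says.** **Route A, Prospective follow-up.** "Research assistants will work for the zonal health office to identify all births occurring in the study area". The section continues: "Independent of the intervention outreach teams, the research assistants will attempt to contact all newborn-mother pairs within 10-days of birth".

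**Route B, Procedures and Data Collection.** Under Procedures, pairs are recruited "as reported to the study team by Health Extension Workers (HEWs) engaged in the study", and a filter comes before the report: "Newborn-mother pairs who fulfill an initial screening criteria will be reported to the study team at the University of Gondar". The filter is partly in HEW hands: "A checklist of the initial screening criteria will be used by the HEWs and study team". Data Collection agrees with this route; the study team's visits are to "screen, consent, and register new newborn-mother pairs reported by HEWs".

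**Links to the intervention.** Study Design says that the outreach work is done with "HDA members recruited by HEWs under the health centers in the catchment areas of the intervention churches". Of the trained priests and HDA members it says: "Their primary activities will be identification of near-term pregnant and newly delivered women".

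**Timing and analysis.** Procedures starts recruitment a month after the intervention begins. It names the HEWs' routine delivery registers as the tracing source and includes every reported pair that meets the criteria until the target number is met. The Statistical analysis plan specifies an intention-to-treat comparison of the primary outcomes without covariate adjustment, with variance adjusted for clustering.

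**The concern.** All births found by research staff, and births that HEWs have screened and chosen to report, are not the same population. The plan does not say which one the trial samples.

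The difference matters because this is a cluster trial that enrols participants after allocation. Randomising churches balances the births that occur in them. It does not balance the births that enter the study if entry depends on someone who knows the arm and has a stake in the programme. HEWs who recruit HDA members for the intervention are in that position. If they report more readily the mothers whom outreach has already reached, the enrolled intervention sample contains too many of them. The contrast in exclusive breastfeeding and mid-upper arm circumference is then overstated. Intention-to-treat keeps enrolled pairs in their allocated arm; it does nothing about pairs that were never enrolled.

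The documents describe no blinding of HEWs or recruiters, no record of births not reported, and no comparison of enrolled pairs with all births by arm. As written, a difference in capture between arms would go unseen.

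**Working it through.** **1. The passages side by side**

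| Question | Prospective follow-up | Data Collection and Procedures |
|---|---|---|
| Who finds births? | Research assistants | HEWs, from their own registers |
| Which births? | All in the study area | Those reported |
| Filter before the study team sees them? | None described | Initial screening, with HEWs using the checklist |
| Relation to outreach teams | Contact is independent of them | Intervention-area HEWs recruit their HDA members |

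The first three rows conflict directly. The fourth is a link rather than a literal breach: the outreach teams are priests and HDA members, not HEWs.

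**2. Who knows the arm**

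HEWs who recruit HDA members in intervention catchments must know that their area has the intervention. Knowledge among control-area HEWs is likely, but no section states it.

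**3. Size, as an illustration**

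The plan has no figure of its own on this point to reproduce. The only documented input is the planned difference in exclusive breastfeeding: 70% − 50% = 20 points (Summary, Methods). Every other input is assumed:

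- outreach reaches 60% of mothers in intervention churches;
- exclusive breastfeeding is 75% if reached and 50% if not;
- reached births are reported with probability a, unreached births with probability b.

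True intervention-arm rate: 0.6 × 0.75 + 0.4 × 0.50 = 0.650.

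Share reached among those enrolled: s = 0.6a / (0.6a + 0.4b).

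Rate among those enrolled: 0.75s + 0.50(1 − s).

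| a / b | s | Enrolled rate | Bias |
|---|---|---|---|
| 0.90 / 0.70 | 0.54 / 0.82 = 0.659 | 66.5% | +1.5 points |
| 0.90 / 0.60 | 0.54 / 0.78 = 0.692 | 67.3% | +2.3 points |
| 0.95 / 0.50 | 0.57 / 0.77 = 0.740 | 68.5% | +3.5 points |

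Against the 20-point target this is 1.5/20 = about 7% to 3.5/20 = about 18%. The control arm has no outreach and so no matching shift in this model.

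**4. When the bias vanishes**

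In general, bias = (s − 0.6) × (rate if reached − rate if unreached). It is zero if a = b, because then s = 0.6, and zero if reached and unreached mothers have the same outcome. Both conditions are unknown.

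No size is given for mid-upper arm circumference. It would need a further assumed gap between reached and unreached infants, and the documents supply neither that gap nor a standard deviation.

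**The case against.** The case for leaving the plan alone has real substance.

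- **Registers and consecutive inclusion are already there.** Procedures names routine delivery registers and takes every reported pair that meets the criteria, by what appears to be the same route in both arms. This stands and lowers the risk. It does not cover births that are never reported.
- **Most criteria are factual.** Biological mother, parish membership, length of residence and date of birth leave little discretion, and the study team screens too. This also stands, but the study team cannot restore a pair it never hears of.
- **The independence clause is narrow.** It covers the research assistants' contact with pairs, relative to the outreach teams. Research assistants could work from HEW registers without breaching it. A reader might infer that the HEW route flatly contradicts promised independence. The documents do not go that far: the direct conflict is all births against reported, pre-screened births.
- **The outreach channel is not documented.** A reader might infer that priests and HDA members feed births to intervention HEWs, giving them a source that control HEWs lack. No section says so. Study Design describes finding women in order to visit and educate them, and HDA members also deliver routine care in control communities. The channel is possible, no more.
- **The illustration assumes the point in dispute.** The reporting gap is an input to the arithmetic. That is correct, and the figures should carry no more weight than that.

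**Conclusion.** The sections conflict on the sampling frame and must be reconciled. Following Procedures as written leaves selection before enrolment partly with workers who, in the intervention catchments, are tied to the intervention and know their arm. The planned primary analysis cannot correct for that, so the plan should be changed.

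The conclusion is a risk of selection bias, not a finding of it. It would be tempting to call all HEWs unblinded, or to say that recruitment will differ by arm. The documents support neither: there is no blinding statement at all, and control HEWs' knowledge is inferred. If outreach pairs do pass births to HEWs, the risk grows, but that remains a conditional.

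The 1.5 to 3.5 point range shows what plausible-looking inputs would do. It is not an estimate or a bound. It rests on assumed reach, assumed reporting probabilities and an assumed 25-point gap between reached and unreached mothers.

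**What to change.** Make the rule in Prospective follow-up the governing one, and bring Data Collection and Procedures into line with it:

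1. In both arms, take every birth in the delivery registers that Procedures already names, with HEWs reporting all births and applying no screen.
2. Have the study team alone apply the eligibility checklist.
3. For each church, log births, contacts within 10 days, eligible pairs and consents, and compare these proportions by arm.

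The log has to be in place before recruitment, because births that were never recorded cannot be reliably reconstructed later.

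**Cost.** Protocol wording, a per-church log, and some extra screening for the study team of births that HEWs would have filtered out. The documents give no staff numbers, so that workload cannot be sized here.

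**What remains.** HEWs still keep the registers. The log would show differential capture among registered births, but it does not remove all dependence on HEWs, and a birth that is never registered stays invisible.

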**Methods:** The study utilizes a community-randomized trial design in which 11 communities will be randomized to receive the intervention and 11 communities will be randomized as control communities. The unit of randomization at the house of worship. The target population for this undertaking is pregnant women and women who recently delivered in rural communities in the North Gondar region of Ethiopia. Infants enrolled in the study will have a baseline evaluation within 10 days of birth and the primary outcomes of mid-upper arm circumference (MUAC) and exclusive breastfeeding will be measured at a follow-up visit at between 5 and 6 months after birth. The sample size of 150 infants from intervention churches and 150 infants from control churches is based on identifying a statistically significant difference of  $\geq 0.2$  cm in mid-upper arm circumference (MUAC) with 80% power at  $\alpha=0.05$ , anticipating 20% of participants being lost to follow-up. We will also have 80% power to detect a significant difference of 50% exclusive breastfeeding at 5-months in the control group versus 70% in the intervention group.

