## **Statistical analysis plan**

We will compare infant outcomes between children exposed to the intervention and those in control communities. We will use logistic regression to compare dichotomous outcomes (e.g., exclusive breastfeeding through 6 months, completion of vaccinations, infant hospitalization) and linear regression for continuous outcomes (e.g., mid-upper arm circumference). Primary outcomes will be evaluated using an intention-to-treat analysis without adjustment for other covariates. We will account for correlation within church communities by adjusting the variance for the effect of clustering.

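### Does the Procedures section place pairs in arms by whether the parish received the intervention, against the intention-to-treat analysis?

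*Combined protocol and SAP*

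**What the plan says.** The Summary (Methods) states that "11 communities will be randomized to receive the intervention", with 11 more randomised as controls, and gives the house of worship as the unit. The Study Participants section agrees: "Parishes will be randomized to receive an outreach intervention". Study Design has churches randomly assigned and contrasts pairs in the catchments of intervention churches with pairs in control churches.

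Procedures describes how an enrolled pair falls into an arm: "Those pairs who attend church at a parish that received the intervention will be assigned to the intervention arm", while "those from the parishes where no intervention was conducted will be assigned to the control arm". On timing, it says "Recruitment will start one month following the start of the intervention".

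The Statistical analysis plan opens with "We will compare infant outcomes between children exposed to the intervention and those in control communities" and then says "Primary outcomes will be evaluated using an intention-to-treat analysis", unadjusted for covariates and with the variance adjusted for clustering by church community.

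**The concern.** Intention-to-treat in a cluster trial means that each pair is analysed in the arm to which its cluster was randomised, whatever happened there afterwards. The Procedures wording depends instead on whether the intervention was received or conducted, and it does not mention the randomised arm. The word exposed in the Statistical analysis plan points the same way.

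The two rules could differ in practice. Study Design says only that priests and Health Development Army members will be asked to take part. Pairs are enrolled after the intervention has begun, so delivery status could be known when a pair is classified. At the level of the mother, "Priests and HDA members will offer women and their families an opportunity to decline individual counseling", and the questionnaire records exposure, so the data for an as-exposed comparison will exist. Study Design also links a pair to a church by catchment area, whereas Procedures uses the church attended.

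If the literal rule were applied and some parishes did not deliver, an event after randomisation would decide arm membership. Parishes that fail to deliver may also differ in breastfeeding. With 11 clusters per arm, moving one parish changes 11 v 11 into 10 v 12.

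**Working it through.** **1. What the text settles**

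| Question | Where | Answer |
|---|---|---|
| What is randomised? | Summary; Study Participants | Community, parish or house of worship |
| How are pairs grouped? | Study Design; Summary sample size | Intervention churches v control churches |
| How are pairs classed at enrolment? | Procedures | Parish received the intervention, or none was conducted there |
| How are primary outcomes analysed? | Statistical analysis plan | Intention-to-treat |
| Does a non-delivering parish change arm? | Nowhere | Not described |

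Three of the four sections that address arm membership or analysis rest on random assignment or name intention-to-treat. The fourth, Procedures, fits them if received the intervention means randomised to it. The one-month lag before recruitment accounts for the past tense. In the sentence about exposed children the comparator is control communities, so a mother in an intervention parish who declines counselling has no route into the control group.

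**2. The plan's own figures**

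300 enrolled × (1 − 0.20) = 240 completers, which matches the Number of Subjects table. The breastfeeding target is 50% v 70%, a 20-point difference. Neither figure depends on how the arm sentence is worded.

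**3. What the literal rule would do**

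The following are assumptions, not figures from the documents: equal parish sizes; k parishes in each arm with breastfeeding d points below the rest; and the k low-rate parishes in the intervention arm are exactly those that deliver nothing.

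*No true effect.* By randomised arm, each arm has k low-rate parishes, so the expected difference is 0. By the literal rule, the intervention group has 11 − k parishes, none low-rate, and the control group has 11 + k parishes, 2k of them low-rate. The spurious difference is 2kd/(11 + k).

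| k | d = 10 | d = 20 |
|---|---|---|
| 0 | 0 | 0 |
| 1 | 20/12 = 1.7 points | 40/12 = 3.3 points |
| 2 | 40/13 = 3.1 points | 80/13 = 6.2 points |

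*True 20-point effect where delivered.* By randomised arm the expected difference is 20(11 − k)/11: 18.2 points for k = 1 and 16.4 for k = 2. By the literal rule it is 20 + 2kd/(11 + k): 21.7 or 23.3 for k = 1, and 23.1 or 26.2 for k = 2.

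*Two-sided 5% error rate.* Take 240 completers split 10:12 or 9:13, a 50% rate, and design effect 1 + (240/22 − 1) × ICC, with an assumed ICC of 0 to 0.05. The standard error is 6.5 to 7.9 points for k = 1 and 6.6 to 8.0 for k = 2. The error rate is P(|Z| > 1.96) with the mean of Z equal to bias/SE.

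| k | d = 10 | d = 20 |
|---|---|---|
| 1 | 5.5–5.8% | 7.0–8.1% |
| 2 | 6.7–7.6% | 12.0–15.5% |

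The upper ends use ICC = 0, which contradicts the scenario, because parishes that differ by d must have a positive ICC. The implied value is d²(k/11)(1 − k/11)/0.25. For d = 0.20 this is 0.013 at k = 1 and 0.024 at k = 2, and the error rates are then about 7.7% and 13.5%.

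**4. What has to happen for any bias under no effect**

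The literal rule must be used in place of intention-to-treat, a parish must deliver nothing at all (partial delivery still counts as received), and such parishes must differ in their underlying breastfeeding rate. If non-delivery is unrelated to that rate, the expected bias with no true effect is zero.

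**The case for a change.** The strongest case for a change is that no sentence says outright that a pair is analysed by its parish's randomised arm whether or not delivery took place. The most explicit sentence on classing an enrolled pair uses delivery language. With few clusters, a choice between two readings made after outcomes are known would be open to challenge, and under the assumptions above the literal rule overstates the effect. A family living in one church's catchment and attending another church also has no explicitly defined arm. A clarifying sentence would cost almost nothing.

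The wording criticism stands: the sentence is loose. The inference that an as-treated comparison is planned does not. Intention-to-treat is named for the primary outcomes, and an analyst who moved a randomised parish to control would be departing from the plan. Complete non-delivery is also made less likely by the design, since Health Development Army members are recruited separately from the priests and the study team monitors delivery by regular visits. The opt-out covers individual counselling only; outreach also takes place at services and community events.

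The difference between catchment and church attended is a real gap in detail. But enrolled families must be Orthodox parishioners with a soul father, and sites are to be reasonably far apart, so pairs straddling two arms should be uncommon. Analysts can fix parish membership sensibly within the stated design.

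**Conclusion.** No change to the plan follows. The delivery wording is most likely shorthand for the randomised arm, and the sections on randomisation and analysis already lead to the sound comparison. The bias is zero if every randomised parish delivers something, and zero in any case if the stated intention-to-treat analysis is followed.

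The illustrative biases of 1.7 to 6.2 points rest on assumed values of k and d and on non-delivery falling exactly on the low-rate parishes. The documents give no basis for any of these. For one non-delivering parish, the 1.7 or 3.3 points are small beside the planned 20. Rewording would make explicit what a competent analyst would do anyway; it would not alter the design, the sample size or the primary analysis.

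### A pair's arm is set at enrolment, after outreach has begun, from the church it attends and whether outreach took place there, rather than from the random allocation of the church the family belonged to beforehand

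*Combined protocol and SAP*

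**What the plan says.** The Summary makes the church the randomised unit ("The unit of randomization at the house of worship"), with 11 communities per arm. Under Study Participants, too, it is parishes that are randomised.

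Arms are explicitly given to individual pairs only in Procedures, directly after the consent step and before baseline data: "Those pairs who attend church at a parish that received the intervention will be assigned to the intervention arm". The counterpart for the comparison group is worded the same way, by what took place in the parish: "those from the parishes where no intervention was conducted will be assigned to the control arm". Pairs are enrolled within 10 days of delivery, and "Recruitment will start one month following the start of the intervention".

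Study Design describes recipients in other terms: "Newborn-mother pairs in the catchment areas of the intervention churches will receive the intervention". It sets them against pairs belonging to control churches, who get the usual community health care. It does not define a catchment. It also says that "pre-planned visits of parishioners' families will be done by the respective priests and the partnering HDA members during the last month of pregnancy", with further visits just after delivery and around baptism, and teaching at religious and community gatherings.

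The statistical analysis plan specifies an unadjusted intention-to-treat analysis with a variance corrected for church clustering. It introduces the comparison as one between exposed children and children in control communities. It does not say how a pair is linked to a randomised church.

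**The concern.** In a cluster-randomised trial, the cluster and arm of each participant should be fixed by something the intervention cannot alter. The Procedures rule departs from this in two ways.

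First, it uses attendance in the present tense, at a visit that follows the planned prenatal and delivery visits. If outreach by an active church draws families in, those families move into the intervention arm after randomisation. They may also differ in how they feed and care for their infants.

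Second, it words the arm by whether the parish received the intervention. A parish allocated to the intervention where priests declined or outreach never took place would literally fall into the control arm. That is an as-treated grouping of clusters, and it conflicts with the planned intention-to-treat analysis.

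Both primary outcomes, MUAC and exclusive breastfeeding, rest on this label, and the clustered variance needs the same link from pair to church.

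**Working it through.** **Order of events for one pair.** (1) The church is randomised. (2) Outreach starts. (3) The family is due a home visit in the last month of pregnancy and another just after delivery. (4) Within 10 days of birth the study team visits, obtains consent and assigns the arm from the parish attended. Step 4 comes after steps 2 and 3, and no section records parish membership between steps 1 and 2.

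**What the other criteria fix.**
- "Mother must have lived in the study area for at least 6 months": the study area contains both arms, so this does not tie a mother to one church.
- EOC membership and a soul father: these require a parish tie, but no date for it and no link to a particular randomised church.
- Exclusion of families planning to relocate: this looks forward from enrolment and concerns residence.
- Sites reasonably far apart: this makes movement less likely, but no distance is given.
- Intention to treat: this cannot be carried out until each pair has a defined church.

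**Size of the delivery problem.** The inputs are 150 infants per arm and 11 churches per arm (Summary). Equal cluster size is my assumption. One church holds 150/11 = 13.6 infants, or 1/11 = 9.1% of its arm. If one allocated parish were not reached, the literal rule would turn 11 versus 11 churches into 10 versus 12, and 150 versus 150 infants into about 136 versus 164.

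**Size of the selection problem.** Suppose a share *s* of the labelled intervention arm joined because of outreach, and their exclusive-breastfeeding rate would in any case be *d* points above that of the rest of the arm. The arm's rate then rises by *s* × *d* with no true effect. The documents give neither *s* nor *d*, and a larger sample would not remove the shift.

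**The plan's own figures, and a dilution illustration.** 120/(1 − 0.20) = 150 per arm matches the 240 completers. For 50% versus 70% at two-sided 0.05 (sidedness assumed), 80% power needs 93 per arm without clustering, and 120 per arm gives 89%. The stated 80% therefore implies an unstated design effect of 120/93 = 1.29. For MUAC, 80% power implies an SD of 0.2/[(1.960 + 0.842) × √(2/120)] = 0.553 cm, which is also unstated. With these back-solved values, suppose a share *q* carries the wrong label. The difference shrinks by (1 − *q*) if only the intervention arm is affected, or by (1 − 2*q*) if both are.

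| *q* (assumed) | Arms affected | MUAC difference | Breastfeeding | Power, either outcome |
|---|---|---|---|---|
| 5% | intervention only | 0.19 cm | 50% v 69% | about 76% |
| 5% | both | 0.18 cm | 51% v 69% | about 71% |
| 10% | intervention only | 0.18 cm | 50% v 68% | about 71% |
| 10% | both | 0.16 cm | 52% v 68% | about 61% |

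The table is purely illustrative. It describes labels that disagree with exposure. A family drawn into an intervention church and visited there is exposed and labelled as exposed, which is selection and not dilution.

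**The case against.** The best defence is that the plan has one coherent unit, the parish. Priests visit their own parishioners, eligibility requires parish membership, and a soul father is a standing tie. Nothing suggests that families change parish because of outreach, and Procedures does not say that parish is first ascertained at the enrolment visit. The questionnaire also asks about exposure to the intervention, so crossover can be described.

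Much of this stands, and it rules out stronger readings that a reader might infer:

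- *That there are two competing rules for arm.* Only Procedures assigns arms. Study Design describes who is reached, and it sets pairs in the catchments of intervention churches against those in the control churches. Catchment there most naturally means parish. The fault is an undefined word.
- *That a family living near one church and attending another falls into opposite arms.* This would follow only if the two churches were allocated differently. Of the other 21 study churches, 10 share the first church's arm, and site spacing lowers the chance further.
- *That both primary comparisons are diluted by a known amount.* The mislabelling rates are assumed, and symmetric dilution does not match a one-way draw into intervention churches.

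The defence does not supply a date for membership, or a statement that arm follows allocation whatever was delivered. Those gaps remain even if catchment means parish.

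**Conclusion.** The concern holds as a defect in the assignment rule. The arm is read after outreach has begun, from current attendance and from whether the parish received the intervention, when it should come from the random allocation of the family's pre-outreach church. The second element conflicts with intention to treat on its face. The first leaves open a route to selection bias that is plausible but undocumented.

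The size of any bias cannot be estimated from the documents. The one concrete figure is that each undelivered parish would move about 9% of the intervention arm, assuming equal clusters. The power figures are not a measured loss, and correcting the rule would not recover them. Keeping families under their earlier church, and undelivered parishes under their allocation, accepts some dilution in return for freedom from selection. The case for change rests on bias, and on making the planned analysis executable.

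**What to change.** Use one rule in Study Design and Procedures, and have the statistical analysis plan refer to it for both the comparison and the clustered variance. Suggested wording:

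*A pair's cluster and arm are the randomised allocation of the church of which the family was a parishioner (for example, the soul father's church) before outreach could reach it. This is the church at randomisation or, for a mother who came to the study area later, the parish she first joined on arrival. It applies whether or not the intervention was delivered there and whichever church is attended at enrolment.*

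The clause on later arrivals is needed because a mother can meet the six-month residence criterion and still have had no parish in the area at randomisation. If the six months are counted at enrolment and she joined on arrival, her parish predates the first planned home visit by about 6 months less 10 days less 1 month, or more than four months. Teaching at gatherings could still have come first, so report how many pairs are classified this way.

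Define catchment, or replace it with parish. Record current attendance and residence, and report the number of discordant pairs by arm. Treat any analysis that excludes them as descriptive only, because current attendance is measured after randomisation and conditioning on it can bring back the selection.

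The cost is wording changes and one or two screening questions, with no extra participants. Any pairs who changed church are analysed under their earlier one.
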